9.1.5. Compensation, Insurance and Indemnity

Information regarding compensation, insurance, and indemnity is addressed in the Clinical Trial Research Agreement.

9.1.6. Study Files and Retention of Records

The Investigator must maintain adequate and accurate records to enable the conduct of the study to be fully documented and the study data to be subsequently verified. These documents should be classified into 2 separate categories including (although not limited to) the following: (1) Investigator's study file, and (2) Subject clinical source documents.

The Investigator's study file will contain the protocol/amendments, IRB/EC approval, informed consent, drug accountability records, staff curriculum vitae, medical licenses as applicable, financial disclosure forms, local laboratory documentation, screening and enrollment log, and other appropriate documents and correspondence.

Subject clinical source documents would include (although is not limited to) the following: Subject hospital/clinic records, physician's and nurse's notes, laboratory reports, worksheets, consultant letters, etc.

All clinical study documents must be retained by the Investigator until the number of years specified in the clinical trial agreement. The Investigator must notify scPharmaceuticals prior to destroying any clinical study records.

Should the Investigator wish to move study records to another location, arrangements must be made to store these in sealed containers so that they can be returned sealed to the Investigator in case of a regulatory audit. Where source documents are required for the continued care of the Subject, appropriate copies should be made for storage outside of the site.

9.1.7. Case Report Forms

For each Subject who signs informed consent, a CRF must be completed and signed (or electronically signed if eCRF) by the principal Investigator or sub-Investigator within a reasonable time period after data collection. This also applies to records for those Subjects who fail to complete the study. If a Subject withdraws from the study, the reason must be noted on the CRF. If a Subject is withdrawn from the study because of a treatment-limiting AE, thorough efforts should be made to clearly document the outcome.

9.1.8. Protocol Deviations

Neither the Investigator nor the Sponsor is permitted to intentionally deviate from the protocol without proper notification to the FDA or to other relevant regulatory authorities in the form of a protocol amendment. Protocol deviations that occur during the study must be documented.

The Investigator will not alter this study protocol without obtaining the written agreement from the sponsor. Once the study has started, amendments should be made only in exceptional cases. The changes then become part of the study protocol and will require re-approval of the Institutional Review Board (IRB/Independent Ethics Committee (IEC)).

9.1.9. Disclosure of Data

The Principal Investigator agrees by his/her participation that the results of this study may be used for submission to national and/or international registration and supervising authorities. If required, these authorities will be provided with the name of the Principal Investigator, their addresses, qualifications and extent of involvement. It is understood that the Principal Investigator is required to provide scPharmaceuticals with all study data, complete reports, and access to all study records.

Data generated by this study must be available for inspection by the US FDA and other regulatory authorities, by scPharmaceuticals and its designees, and the IRB as appropriate. At a Subject's request, medical information may be given to his or her personal physician or other appropriate medical personnel responsible for his or her welfare. Subject medical information obtained during this study is confidential and disclosure to third parties other than those noted above is prohibited.

9.1.10. Financial Disclosure

The US FDA Financial Disclosure by Clinical Investigators (21 CFR 54) regulations require Sponsors to obtain certain financial information from Investigators participating in covered clinical studies; each Principal Investigator and Sub-investigator is required to provide the required financial information and to promptly update scPharmaceuticals with any relevant changes to their financial information throughout the course of the clinical study and for up to 1 year after its completion. This rule applies to all Principal Investigators and Sub-investigators participating in covered clinical studies to be submitted to the FDA in support of an application for market approval.

9.1.11. Study Completion

scPharmaceuticals requires the following data and materials before a study can be considered complete or terminated:

1. All clinical data and special test results from screening through the end of the study.
2. eCRFs properly completed by appropriate study personnel and signed and dated by the Principal Investigator.
3. Complete Product Accountability records.
4. Copies of protocol amendments and IRB approval/notification/closure if appropriate.

9.1.12. Drug and Device Product Accountability

The Investigator or designee (pharmacist) is responsible for ensuring adequate accountability of all used and unused study treatment. This includes acknowledgment of receipt of each shipment of study treatment (quantity and condition) and Subject dispensing records and return. Dispensing records will document quantities received and quantities dispensed to Subjects, including lot number, date dispensed, Subject identifier number and the initials of the person dispensing the medication.

At the end of the study, following final product reconciliation by the monitor, the Sponsor will instruct the study site the handling of all used and unused study drugs and materials.

9.1.13. Inspections

The Investigator will provide access to source documents and all study records for this trial to appropriately qualified personnel from scPharmaceuticals or its representatives, and to regulatory authority inspectors.

9.2. Sponsor Responsibilities

9.2.1. Study Materials and Instructions

It is the Sponsor's responsibility to ensure that the Investigator is provided with the documents and other study materials necessary to conduct the study. Examples of those materials include, but are not limited to protocol, Investigator's Brochure, study treatments, CRF, logs, etc. The Sponsor or designee will also provide training and oversight through site and medical monitoring.

9.2.2. Protocol Modifications

Protocol modifications, except those intended to reduce immediate risk to study Subjects, will be made by Sponsor-initiated amendment. IRB approval must be obtained before changes can be implemented.

9.3. Joint Investigator and Sponsor Responsibilities

9.3.1. Access to Information for Monitoring

In accordance with International Conference on Harmonization Good Clinical Practice (ICH-GCP) guidelines, the study monitor must have direct access to the Investigator's source documentation in order to verify the data recorded in the CRFs for consistency.

The monitor is responsible for routine review of the CRFs at regular intervals throughout the study, to verify adherence to the protocol, and the completeness, consistency and accuracy of the data being entered. The monitor should have access to any Subject records needed to verify the entries on the CRFs. The Investigator agrees to cooperate with the monitor to ensure that any problems detected during these monitoring visits are resolved.

9.3.2. Study Discontinuation

Both the Sponsor and the Investigator reserve the right to terminate the study at any time. Should this be necessary, both parties will arrange discontinuation procedures and notify the appropriate regulatory authority(ies), IRBs and IECs. In terminating the study, the Sponsor and the Investigator will assure that adequate consideration is given to the protection of the Subjects' interests.

11. APPENDICES

11.1. Appendix 1. Time and Event Schedule

[figure not shown]
	Screening Phase Day -14 to -3	Baseline Phase Assessment Day 0	Treatment Phase						Follow-Up Phase Day 5 ± 1 ¹⁴		
			Crossover Period 1			Washout Period (3 ± 1 Days)	Pre-Period 2 Assessment Day 3 ± 1	Crossover Period 2			
			Day 0					Day 3 ± 1			
			Pre-dose	Dosing	Post-dose			Pre-dose		Dosing	Post-Dose
Sign Informed Consent	X										
Confirmation of Eligibility	X	X									
Med History & Demographics	X										
Complete Physical Examination ¹	X							X			
Limited Physical Examination ¹		X		X	X		X				
Screening Labs for Eligibility ²	X										
Weight	X	X		X	X		X	X			
Height (Screening only) ³	X										
Blood Alcohol Test	X										
Alcohol Breath Test		X			X						
Temperature	X	X			X						
Blood Pressure and Heart Rate	X	X		X	X		X	X			
Clinical Laboratory Tests ⁴		X		X	X		X				
Urine Drug Screen	X	X			X						
Serum Pregnancy Test ⁵	X										
Urine Pregnancy Test ⁵		X			X						
12-lead ECG	X										
Admission to CRU		X			X						
Randomization to Treatment Sequence		X									
Study Treatment Administration ⁶			X			X					
Plasma for Pharmacokinetics ⁷			X	X		X	X				
Void Bladder ⁸			X			X					
Urine Collection ⁸				X			X				
Food and Fluid intake ⁹				X			X				
Assessment of Injection Site Pain ¹⁰			X	X		X	X				
Photograph of Injection Site ¹¹			X	X		X	X				
Adverse Events ¹²				X	X	X	X	X			
Prior Medication Assessment	X	X									
Concomitant Medications				X	X	X	X	X			
Schedule Next Study Visit	X			X			X				

Discharge from CRU ¹³						X						X	
----------------------------------	--	--	--	--	--	---	--	--	--	--	--	---	--

- ¹ A complete/full physical examination should be performed at Screening and Follow-up. On Days 0 and 3 a limited physical examination may be performed consisting of assessments of the skin, lungs/chest, heart, extremities and abdomen and any other abnormalities detected during the study period. Post-dose physical examination on Day 0 and Day 3 should be performed 12 hours after the study drug is administered.
- ² Screening labs include sodium, potassium, calcium, chloride, magnesium, carbon dioxide, blood urea nitrogen (BUN), serum creatinine, glucose, hemoglobin, hematocrit and blood alcohol.
- ³ Height and weight collected for calculation of BMI. Height collected at Screening only.
- ⁴ Clinical labs include sodium, potassium, calcium, chloride, magnesium, carbon dioxide, blood urea nitrogen (BUN), serum creatinine, glucose, hemoglobin, and hematocrit. Post-dose clinical labs on Day 0 and Day 3 should be performed 12 hours after the study drug is administered.
- ⁵ Pregnancy test for females of child-bearing potential.
- ⁶ Intravenous furosemide is administered as 40 mg over 1 to 2 minutes followed by a second dose of 40 mg over 1 to 2 minutes, 2 hours apart by IV injection. SCP-111 is administered as a single, 80-mg dose by subcutaneous injection via an autoinjector.
- ⁷ Pharmacokinetic sampling per instructions in 6.2.2.6
- ⁸ Subjects will be instructed to void immediately before dosing (pre-dose urine) and this sample will be discarded. Urine from spontaneous voids during post-dose phases will be collected and pooled, measured, recorded for time periods (0-1), (1-2), (2-3), (3-4), (4-5), (5-6), (6-7), (7-8), (8-10) and (10-12) hours after initiation of dosing. Urine from each collection period must be collected in a single vessel and refrigerated until the end of the collection period. Urinary sodium and urinary potassium concentrations for each collection interval over the 12-hour urine collection period will be analyzed by standard lab biochemistry test. Total urine output volume will be documented for each collection period.
- ⁹ Low sodium snacks and meals as well as water, juice, and caffeine free beverages will be allowed ad libitum, and the amount measured and recorded over the post-dose phases. Subjects will be monitored to ensure a minimum of 100 mL of fluid consumed for every 300 mL of urine output.
- ¹⁰ Assessment of injection site pain for IV administration performed pre-dose after IV needle placement, immediately after 1st dose and 15 and 30 minutes after 1st dose, immediately after 2nd dose and 15 and 30 minutes and 4 and 10 hours after the 2nd dose. For SC administration, injection site pain conducted pre-dose, immediately after dose and 15 and 30 minutes and 6 and 12 hours after dose.
- ¹¹ Photographs of the injection site will be performed prior to the IV and SC injection (baseline) and 4 hours post IV administration or 6 hours post SC administration. In addition, a photograph will be taken of the IV and SC injection site for any AE (i.e., erythema, edema, pruritus, bruising) that occurs at the site at the time of the event.
- ¹² AEs will be assessed continuously during administration of study drug and during the post-dose phase. AEs and SAEs will be followed until resolution if the nature of the AE or SAE requires continued monitoring at the discretion of the Investigator.
- ¹³ Discharge from the CRU after the last assessment per protocol if safety parameters acceptable to Investigator.
- ¹⁴ Follow-up should occur 24-48 hours after discharge from CRU for Crossover Period 2.

11.2. Appendix 2. Assessment of Injection Site Pain

INJECTION SITE PAIN ASSESSMENT SCALE

Verbally indicate the number on the Numeric Rating Scale that best represents the intensity of pain at or around the injection site NOW, with 0 being None and 10 being the worst possible pain.

Sequence	The order in which a subject receives different treatments during the crossover study. For example, Sequence 1 might involve receiving IV furosemide first followed by SC SCP-111, while Sequence 2 might involve the reverse order.
T_{max}	Time to Maximum Concentration
λ_z	Terminal Elimination Rate Constant
$t_{1/2}$	Terminal Half-Life
UO	Urine Output
$V_{z/F}$	Apparent Systemic Volume of Distribution
V	Systemic Volume of Distribution

1. TITLE

Open-label, Single-dose, Randomized, Two-way (two-period) Crossover Study to Compare the Pharmacokinetics and Pharmacodynamics of SCP-111 (furosemide injection) Administered as a Subcutaneous Injection vs Furosemide Administered as an Intravenous Injection in Healthy Volunteers.

2. STUDY DESIGN

This is an open-label, single-center, single-dose, randomized, two-way (two-period) crossover study in healthy volunteers. Each Subject will complete Screening, Baseline, Treatment (two cross-over periods), and Follow-up Phases.

The Screening Phase will be conducted on an outpatient basis between 14 and 3 days prior to the Baseline visit. Subjects will be instructed to maintain a < 2-gram sodium diet and abstain from caffeine-containing products within 2 days prior to admission to the Clinical Research Unit (CRU). On arrival to the CRU (Day 0), baseline and final qualification assessments will be performed.

The Treatment Phase will be comprised of two crossover periods separated by a 3 ± 1 day washout period. During each CRU admission and through the washout period, Subjects will continue a < 2-gram sodium diet and abstain from caffeine-containing products. At baseline (Day 0), subjects will be randomly assigned in a 1:1 ratio to 1 of 2 treatment sequences to receive intravenous (IV) furosemide or subcutaneous (SC) SCP-111 in the abdomen in Crossover Periods (i.e., IV followed by SC or vice versa). Blood samples will be collected to measure furosemide plasma concentrations at pre-dose and for 12 hours post-dose. Prior to dosing in each Treatment Phase, subjects will void their bladder completely and urine will be collected starting after the injection through 12 hours post injection to determine total urine output and urinary sodium and potassium excretion. Assessment of injection site pain will be conducted for IV and SC administration using an 11-point pain scale. Photographs of the injection site will be performed prior to the IV and SC injection (baseline) and 4 hours post IV administration and 6 hours post SC administration. In addition, a photograph will be taken of the IV and SC injection site for any adverse event (AE) (i.e., erythema, edema, pruritus, bruising) that occurs at the site at the time of the event. Subjects will remain domiciled in the CRU for each Treatment Phase through 12 hours after administration of study drug. After final assessments are performed, subjects may be discharged from the CRU if safety parameters are acceptable to the Investigator.

The Follow-up Phase will occur 24-48 hours (Day 5 ± 1) after discharge from the CRU following Crossover Period 2, completing Subjects' study participation.

1. TREATMENT

Study Drug:

- Intravenous Furosemide (IV Furosemide): Hospira, furosemide injection, solution 10 mg/mL (NDA 018667) (total dose = 80 mg) administered

intravenously 40 mg over 1 to 2 minutes by IV injection followed by a second dose of 40 mg over 1 to 2 minutes, 2 hours later (reference treatment).

- SCP-111 (furosemide injection), 80 mg/1 mL for subcutaneous administration: Total dose = 80 mg; administered as a subcutaneous injection (test treatment) via an autoinjector.

SCP-111, (furosemide injection), 80 mg/1 mL is a proprietary furosemide formulation that is isotonic and buffered to a neutral pH for subcutaneous administration.

Study Device: SCP-111 Autoinjector is an investigational single-entity drug-device combination product consisting of a prefilled syringe containing 1 mL of SCP-111 (furosemide injection), preloaded into a fixed single dose, disposable, two step mechanical autoinjector designed to administer the full dose to the subcutaneous tissue.

2. SAMPLE SIZE

In one study, the average coefficient of variation for furosemide AUC_{inf} following a 20 mg dose by the intravenous, oral, and sublingual routes of administration were 50%, 25%, and 33%, respectively ([Haegeli, et al. 2007](#)). In another study, the coefficient of variation for AUC_{inf} following 2-40 mg intravenous doses 2-hours apart was 31.6% and 30.6% for an 80 mg, 5-hour subcutaneous infusion ([Sica DA, et al. 2018](#)).

Assuming an intra-subject variability is approximately $\frac{1}{2}$ of total variability for the primary pharmacokinetic parameter AUC_{inf} and the test reference would fall within 95% to 105% at a significance level of 0.05, a minimum sample size of 18 subjects would be required to establish bioequivalence between test and reference products (defined as 90% CI for AUC_{inf} Geometric mean ratio SC injection to IV injection of furosemide within 80-125% interval) with a priori statistical power of at least 90%.

21 subjects will be enrolled to ensure 18 subjects complete the study through the Follow-up Phase.

3. OBJECTIVES

3.1. Primary Objective:

To estimate the bioavailability of SCP-111 80 mg/1 mL administered as a subcutaneous injection via an autoinjector compared with an equivalent dose of furosemide administered as two 40 mg intravenous injections over one to two minutes, two hours apart.

3.2. Secondary Objectives:

- To describe the pharmacokinetics and pharmacodynamics of SCP-111 80 mg/1 mL administered as a subcutaneous injection via an autoinjector.
- To describe the safety and tolerability of SCP-111 80 mg/1 mL administered as a subcutaneous injection via an autoinjector.

4. DATA ANALYSIS CONSIDERATION

4.1. General Data Considerations:

The following conventions will be applied to analyses/data presentation:

All dates will be displayed in DDMMYYYY format.

Repeat assessments will be considered unscheduled. Unscheduled visit data will be presented in Listings, but not in Tables and Figures.

For pharmacokinetic analyses, Phoenix® WinNonlin® version 8.2 or higher will be used. The statistical analyses will be performed using SAS release version 9.4 or higher.

All Tables, Listings and Figures (TLFs) will be produced in landscape format. In general, all data collected during the study will be presented in the data listings. Unless otherwise noted, the data will be sorted first by treatment, then by subject number, and then by date within each subject number. The number of variables presented in each listing can vary. Please refer to Mock tables, listings, and figures.

Data will be summarized by treatment where appropriate. The total number of subjects (N) in the treatment under the stated population will be displayed in the header of summary tables.

Data will be summarized using descriptive statistics for continuous variables. Unless otherwise stated, descriptive statistics will include number of subjects (n), mean, standard deviation (SD), minimum, median, and maximum. When n=0, except n, all other summary statistics will be kept blank. In case n=1, only n, minimum and maximum will be reported, and all other summary statistics will be kept blank. The statistic "Missing" will also be evaluated by enumerating the number of missing entries/subjects, if any at that visit, and presented as a summary statistic only for the resulting visits.

For categorical variables, data will be summarized using counts and percentages. The number [n] indicates the actual number of subjects with a particular value of a variable or event, which should always be less than or equal to the total number of subjects in the respective treatment [N]. The number and percentage of subjects with missing values for a variable/category/event will also be presented for the resulting visits under the "Missing" category. Percentage will be obtained by: $\% = (n/m) * 100$, where m is the number of subjects present at that visit. Unless otherwise stated, all percentages will be expressed to one decimal place. The number and

percentage of subjects will always be presented in the form XX (XX.X). Counts of zero in any category will be presented as “0” and if the percentage in any category to be presented is 100, it will be presented as “100”.

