6.2.1.3.3. Post-Dose (Hour 0-12)

The following assessments will be completed beginning after the initial dose:

1. Blood pressure (15, 30 minutes and Hour 1, 2, 2.5, 3, 4, 6, 8 and 12)
2. Heart rate (15, 30 minutes and Hour 1, 2, 2.5, 3, 4, 6, 8 and 12)
3. Plasma sample for pharmacokinetics as described in Section 6.2.2.6
4. Clinical laboratory tests as described in Section 6.2.2.3 (Hour 12)
5. Urine collection from spontaneous voids for time periods (0-1), (1-2), (2-3), (3-4), (4-5), (5-6), (6-7), (7-8), (8-10) and (10-12) hours post-dose for urine volume and urinary sodium and potassium as described in Section 6.2.2.5
6. Food, snack and fluid intake and recording as per Time and Event Schedule
7. Assessment of injection site pain as described in Section 6.2.2.7
8. Adverse events
9. Concomitant medications
10. Limited physical examination as described in Section 6.2.2.1 (Hour 12)
11. Weight measurement (Hour 12)
12. Photograph of Injection Site (4 hours post IV administration or 6 hours post SC administration) as described in Section 6.2.2.8
13. Schedule next study visit
14. Discharge from the CRU if safety parameters are acceptable to the investigator (Hour 12)

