6.2.2.3.2 Pre-Dose and Post-Dose

Blood Clinical Chemistry: sodium, potassium, calcium, chloride, magnesium, carbon dioxide, blood urea nitrogen, serum creatinine, glucose, hemoglobin, hematocrit.

Post-dose clinical labs on Day 0 and Day 3 should be performed 12 hours after the study drug is administered.

The Investigator is responsible for determining if out of range laboratory values are clinically significant or not. All clinically significant values will be followed until stabilization, resolution, or loss to follow-up.

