9.3.4. Other Safety Analyses

9.3.4.1. Clinical Laboratory Evaluation

This section outlines the designated laboratory evaluations to be conducted at predetermined visits during the study and describes how these results will be systematically summarized.

Included Laboratory Tests:

- **Electrolytes and Metabolites:**
 - Sodium (Na⁺)
 - Potassium (K⁺)
 - Calcium (Ca²⁺)
 - Chloride (Cl⁻)
 - Magnesium (Mg²⁺)
 - Carbon Dioxide (CO₂)
 - Blood Urea Nitrogen (BUN)
 - Serum Creatinine
 - Glucose
- **Hematological Parameters:**
 - Hemoglobin
 - Hematocrit

eGFR will be calculated using the simplified Modification of Diet in Renal Disease (sMDRD) equation and included in the clinical laboratory summaries and analyses.

$$\text{eGFR (mL/min/1.73 m}^2\text{)} = 175 \times (\text{Serum Creatinine (mg/dL)})^{-1.154} \times (\text{Age})^{-0.203} \times (0.742 \text{ if female}) \times (1.212 \text{ if African American})$$

Where:

- Serum Creatinine is measured in mg/dL
- Age is in years

All parameters will be summarized using descriptive statistics. Summaries will be provided by the treatment for pre-dose and post-dose in each treatment period. Data will be presented as both raw values and as changes from baseline.

Period-Specific Analysis:

Changes during each treatment period will be evaluated. For Period 1, this involves comparing baseline (Screening or Baseline Assessment (Day 0), if baseline data is missing) with Treatment Crossover Period 1 (Day 0). For Period 2, changes from baseline (Pre-Period 2 Assessment (Day 3 ± 1) to Treatment Crossover Period 2 (Day 3 ± 1) will be assessed.

Frequency tables will classify values as low, normal, or high based on reference ranges. These tables will provide insights into the distribution of values across these classifications.

All abnormal laboratory values will be listed to highlight noteworthy deviations.

Timetable for Laboratory Assessments:

- **Baseline Assessment (Day 0):** Initial laboratory assessments prior to any treatment.
- **Treatment Crossover Period 1 (Day 0):** Laboratory assessments 12 hours after the study drug is administered in the first treatment phase.
- **Pre-Period 2 Assessment (Day 3 ± 1):** Laboratory assessments conducted before the commencement of the second treatment phase.
- **Treatment Crossover Period 2 (Day 3 ± 1):** Laboratory assessments 12 hours after the study drug is administered in the second treatment phase.

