9.3.4.2. Vital Signs

Systolic and diastolic blood pressures (mmHg), heart rate (beats/min), and body temperature (°C) will be summarized with descriptive statistics at each timepoint and changes from baseline including mean, standard deviation, median, minimum, and maximum values.

Data will be analyzed by timepoint for each treatment group (IV and SC). A p-value for between-treatment group comparison will be provided at each timepoint to assess statistical significance of any observed differences.

All data will be listed by treatment, treatment sequence, subject, visit, and time point.

9.3.4.3. 12-lead ECG

ECG parameters will be summarized with descriptive statistics for the overall population at baseline. Data for each subject will be listed.

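### Laboratory abnormalities seen only on an unscheduled or repeat draw, and not reported as adverse events, reach no safety table, because the SAP has no any-time or worst post-dose summary

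*SAP*

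**What the plan says.** SAP 4.1 sets two general rules. The first is "Repeat assessments will be considered unscheduled"; the second is "Unscheduled visit data will be presented in Listings, but not in Tables and Figures". Neither is qualified for safety data. The same section gives missing values their own category in frequency tables.

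For laboratory data, SAP 9.3.4.1 plans descriptive statistics, changes from baseline and a categorical summary: "Frequency tables will classify values as low, normal, or high based on reference ranges". Its timetable has four occasions: the Day 0 baseline, 12 hours after dosing in Period 1, the Pre-Period 2 assessment, and 12 hours after dosing in Period 2. This matches Protocol 6.2.2.3.2: "Post-dose clinical labs on Day 0 and Day 3 should be performed 12 hours after the study drug is administered". The Follow-up visit (Protocol 6.2.1.7) has no laboratory tests. SAP 9.3.4.1 also provides a listing: "All abnormal laboratory values will be listed to highlight noteworthy deviations".

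For vital signs, the schedule in Protocol 6.2.1.3.3 is "Blood pressure (15, 30 minutes and Hour 1, 2, 2.5, 3, 4, 6, 8 and 12", and SAP 9.3.4.2 says the data "will be summarized with descriptive statistics at each timepoint and changes from baseline including mean, standard deviation, median, minimum, and maximum values". There is a p-value at each timepoint but no normal/abnormal classification.

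Abnormal findings have a second route into the report. Protocol 7.7.3 has clinically significant abnormal results recorded as adverse events when they meet the definition, and SAP 9.3.1 tabulates treatment-emergent events by treatment. Protocol 7.1 narrows that route: a laboratory abnormality with no symptoms and no intervention is generally not an adverse event.

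**The concern.** Protocol 1.3 names low sodium, potassium and calcium and a fall in blood pressure as known risks of furosemide, and describing safety and tolerability is a secondary objective. For the electrolytes, the only by-treatment incidence outside the adverse event tables comes from the low/normal/high table, and that table sees one moment after dosing.

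Values from other moments can arise. Protocol 6.2.2.3.2 requires clinically significant results to be followed until they settle, and the site may draw blood when a subject is unwell. Under SAP 4.1 none of these values can enter a table. A reader who takes the low/normal/high table as the share of subjects with any abnormality after each treatment would be reading a count that can miss observed cases.

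**Working it through.** The plan gives no figure on this point, so there is nothing to reproduce. The check sets the schedule against the tabulation rule.

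**1. Scheduled post-dose chemistry.** There is one panel per period, at Hour 12 (Protocol 6.2.2.3.2; SAP 9.3.4.1). Any draw between dosing and Hour 12 is unscheduled. After Hour 12 in Period 1, the next scheduled panel is the Pre-Period 2 assessment, which SAP Section 5 makes the Period 2 baseline. After Hour 12 in Period 2 there is none.

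**2. Where each kind of result ends up.**

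| Situation | Low/normal/high table | Adverse event tables | Listing |
|---|---|---|---|
| Normal at Hour 12; abnormal only on another draw or a repeat; not an adverse event | Normal | No | Yes |
| Normal at Hour 12; abnormal earlier with symptoms or treatment | Normal | Yes, if recorded under Protocol 7.1 and 7.7.3 | Yes |
| Abnormal at Hour 12; normal on repeat | Abnormal | Only if an adverse event | Yes |
| Abnormal at Hour 12; further from normal on repeat | Abnormal, but the more extreme value is not in the summary statistics | Only if an adverse event | Yes |
| No Hour 12 value; abnormal on another draw; not an adverse event | Missing | No | Yes |

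Only the first and last rows lose an observed abnormality from every table.

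**3. Direction.** Let A be the subjects abnormal at the scheduled post-dose draw and B the subjects abnormal at any post-dose draw. A is contained in B, so a count of A can equal or fall below a count of B but never exceed it. As a description of Hour 12 itself, the table is not biased.

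**4. Size.** One subject in the first or last row is 1/21 = 4.8 percentage points of the enrolled number, or 1/18 = 5.6 points of the planned completers. SAP 4.1 uses the number of subjects present at the visit as denominator, so the exact figure depends on attendance. The documents give no rate of unscheduled draws, so the number of such subjects cannot be estimated.

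**5. Blood pressure for comparison.** The scheduled post-dose times are 0.25, 0.5, 1, 2, 2.5, 3, 4, 6, 8 and 12 hours: ten readings, seven of them by Hour 4. The gaps are 0.25, 0.25, 0.5, 1, 0.5, 0.5, 1, 2, 2 and 4 hours, so the longest is 4 hours (Hour 8 to Hour 12). An unscheduled low reading is absent from the timepoint summaries, but no category exists in which it could be misplaced.

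**The case against.** The strongest reply is that extra draws are taken because something is wrong, and those are the cases the adverse event route is built to catch. A low potassium found because of cramps and then corrected has both symptoms and an intervention, so under Protocol 7.1 and 7.7.3 it should be recorded as an adverse event and tabulated by treatment. Every abnormal laboratory value is listed as well, and with about 21 subjects the listings can be read in full. Scheduled-only tables also compare the treatments at like times, whereas extra checks in an open-label study may depend on knowledge of the treatment given.

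Most of this stands, and it narrows the point. It does not cover an out-of-range value without symptoms or intervention, which reaches no table, and a listing gives no incidence by treatment. The open-label argument is a reason to keep the by-timepoint tables on scheduled values and to report how often extra checks were made. It is not a reason to have no any-time summary.

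A reader might infer more than the documents support:

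- **Omitted values are recoded as normal.** No text does this. The subject is classed by the scheduled value, or as missing.
- **A recheck erases an abnormal result.** The scheduled value stays in the table, so the rule also stops a normal repeat from displacing an abnormal original.
- **Low blood pressures are counted as normal.** There is no such classification for vital signs.
- **The loss differs by treatment.** The two regimens differ in timing, so this is possible, but nothing in the documents shows it.

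**Conclusion.** The point holds in a limited form. SAP 4.1 bars repeat and unscheduled values from all tables, and no later section restores them through an any-time or worst post-dose summary. With one scheduled post-dose panel per period, a laboratory abnormality seen only on another draw and not reported as an adverse event is visible only in listings. The effect on a count of any post-dose abnormality can only be downward. Its total size is unknown; each affected subject is 4.8 points (1/21) or 5.6 points (1/18). For blood pressure and heart rate the gap is small.

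Two assumptions matter. First, the SAP 4.1 rule is taken to cover an extra draw made during a CRU stay as well as data from a separate unscheduled visit; the sentence on repeat assessments and the four-occasion timetable in 9.3.4.1 support that reading. Second, some unscheduled draws must occur; if none do, nothing is lost. The bioavailability analysis is unaffected. This is a cheap improvement to a descriptive safety summary.

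**What to change.** Keep all by-timepoint summaries on scheduled values. Then:

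- **SAP 4.1:** state one exception, that unscheduled and repeat values enter the worst post-dose summaries.
- **SAP 9.3.4.1:** add a supplementary by-treatment row for the worst post-dose value in each period: lowest sodium, potassium, calcium and magnesium, and highest creatinine. Use scheduled and unscheduled values from dosing up to, but not including, the Pre-Period 2 assessment, or through Follow-up for Period 2. Classify it low/normal/high by the reference ranges and show it against the category at the period baseline.
- **SAP 9.3.4.2 (optional):** add lowest systolic pressure and highest heart rate on the same basis.
- **Both sections:** report by treatment how many subjects had unscheduled assessments, so that unequal ascertainment in this open-label study is visible.

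The cost is SAP wording and one or two extra shells, with no new data and no change to conduct. The tabulated abnormality rate may be slightly less favourable. A worst-value row also keeps an abnormal value that a repeat did not confirm, so it should be read beside the listing.
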